## 10.2 Statistical Analyses

### 10.2.1 Statistical analysis for the primary objective

*To evaluate the feasibility and efficacy of photobiomodulation therapy (PBM) in reducing oral mucositis in children and adolescents at risk for grade 3 oral mucositis undergoing an allogeneic hematopoietic cell transplant (HCT).*

Hypothesis 1: Children and adolescents will receive 75% of the attempted PMB treatment and will be less likely to develop grade 3 oral mucositis from the 1st day of conditioning to day +20 of transplant or engraftment.

Descriptive statistics (counts, percentages, mean, median, standard deviation and interquartile range) and confidence interval will be calculated for the percentage of successful treatment administered, total days on the protocol, days treatment is received, cumulative dose and the number of treatments received at each site.

The count, percentage and confidence interval will be calculated for allogeneic HCT patients who receive PBM and develop Grade 3 mucositis. Whether the percentage of the prospective sample is significantly different from the historical rate is accessed by the monitoring rule in Section 10.1.

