#### **3.1 Inclusion Criteria**

- 3.1.1 No age limitation
- 3.1.2 To be admitted for an allogeneic hematopoietic cell transplant,
- 3.1.3 All eligible autologous hematopoietic cell transplant, at risk for grade 3 mucositis per transplant service secondary to conditioning regimen or previous history of grade 3 mucositis
- 3.1.4 Dental exam prior to admission, as per preadmission criteria
- 3.1.5 Willingness of research participant to provide assent/consent and parent/ legal guardian/representative to give written informed consent.

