### *Chart Abstraction*

The patient's age, sex, primary diagnosis, transplant type, conditioning regimen, radiation dose, time to engraftment, days of nutritional support, utilization of pain medication, and results of positive oral, nasal and blood cultures during transplant.

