# 10. STATISTICAL CONSIDERATIONS

## 10.1 Sample Size

A review from June 2015 to May 2019, identified 93 first allogeneic transplant patients with similar conditions, and 66 (71%) of them developed grade 3 or above oral mucositis. With an estimated clinically meaningful effect size of 20% for PBM, the estimated percentage of patients who will receive PBM and develop grade 3 oral mucositis is 51%.

St. Jude Children's Research Hospital  
IRB NUMBER: 19-0225  
IRB APPROVAL DATE: 01/28/2021

We will use the two-stage one-arm design with historical controls to monitor both efficacy and futility. The complete historical control sample will be used in both the interim analysis and final analysis. The test statistic in Chang et al [28] treats the historical control sample as if they are the control arm in a two-arm design. Given the relatively small sample size, we did not use the asymptotic distribution of the test statistic. Instead, we used Monte Carlo methods to estimate the sampling distribution of the test statistic under null and alternative hypotheses by 100,000 Monte Carlo data sets. The simulation program is written in R.

The rules of which accommodate both efficacy and futility. The null hypothesis is  $p_0=0.71$ ; the alternative hypothesis is  $p_1=0.51$ ; The type-I error rate = 0.05 and power 0.8 are used.. The detailed information about the two-stage design is shown in the following table. The attained type-I error rate and power are 0.048 and 0.813, respectively.

Loo k #	n	Boundari es		Boundary Crossing Probability (Incremental)			
				Under H0		Under H1	
		Efficac y	Futilit y	Efficac y	Futilit y	Efficac y	Futilit y
1	40	20	29	0.015	0.508	0.526	0.015
2	66	38	39	0.033	0.444	0.288	0.172
Total				0.048	0.952	0.813	0.187

The expected sample size under null and alternative hypotheses is 56 and 51, respectively. In the historical data between July 2015 and May 2016, 24 patients received allogeneic HCT. We estimate that study accrual of 66 transplant patients will be completed in 31 months after study activation.

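### The primary efficacy conclusion rests on an unadjusted comparison with historical controls; a 5- to 10-point case-mix shift would raise the false-positive rate from about 5% to about 15–39%

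*Combined protocol and SAP*

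**What the plan says.** **Primary decision.** Section 10.2.1 plans a count, percentage and confidence interval for grade 3 mucositis. For inference it says only: "Whether the percentage of the prospective sample is significantly different from the historical rate is accessed by the monitoring rule in Section 10.1". The table in Section 10.1 sets efficacy at 20 events in 40 patients or 38 in 66, and futility at 29 in 40 or 39 in 66.

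**Comparator.** Section 10.1 describes "93 first allogeneic transplant patients with similar conditions, and 66 (71%) of them developed grade 3 or above oral mucositis". The whole historical sample is used at both looks, and the test statistic handles it as a control arm. What makes the conditions similar is not defined.

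**Eligibility.** Section 3.1 asks for "To be admitted for an allogeneic hematopoietic cell transplant" and sets no age limit. Section 3.2 does not exclude a second or later transplant.

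**Covariates.** The Chart Abstraction part of Section 6.2 lists "The patient's age, sex, primary diagnosis, transplant type, conditioning regimen, radiation dose", among other items. Section 10.2.2 sends age, sex, primary disease and regimen of the historical patients to the biostatisticians. It matches one control to each PBM patient on these four variables and fits a generalized linear model with them as covariates. The outcomes there are mucositis grade, duration and days to engraftment.

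**The concern.** The comparison is not randomised, so the PBM group and the historical group may differ in expected grade 3 rate for reasons unrelated to PBM. The plan accepts that such differences matter: it matches and adjusts for the secondary outcomes, and Section 3.1 names conditioning regimen as a source of grade 3 risk for autologous patients. Yet the analysis that decides efficacy uses none of this information. The one concrete mismatch in the documents is that controls are first allogeneic transplants while the trial takes any allogeneic transplant.

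If the enrolled patients would have had a lower rate anyway, the rule credits the difference to PBM. Section 1.0 gives the ultimate aim as building PBM into nursing care guidelines, so an efficacy claim that case mix could explain would matter. The trial could also cross the efficacy boundary while its own matched comparison disagreed, and nothing in the plan says how that would be read.

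**Working it through.** **Inputs (Section 10.1).** Controls 66/93 = 0.71; p0 = 0.71, p1 = 0.51; looks at n = 40 and n = 66, with 26 new patients between them; the boundaries above. "The type-I error rate = 0.05 and power 0.8 are used"; and "The attained type-I error rate and power are 0.048 and 0.813, respectively". Sidedness is not stated, but the efficacy boundary lies only on the low-event side, so the rule acts as a one-sided test.

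**Step 1: reproduce the plan's figures.** Let H ~ Bin(93, 0.71) be the control events, X1 ~ Bin(40, p) and X2 ~ Bin(26, p). With a statistic S comparing H/93 with the PBM proportion,

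P(efficacy) = P(S1 ≥ c_E) + P(c_F < S1 < c_E and S2 ≥ c_2),

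summed exactly over H, X1 and X2. The documents do not print the critical values. They were searched within the intervals that the printed counts imply at H = 66 (for the pooled Z at the final look, 38/66 gives 1.749 and 39/66 gives 1.558, so c_2 lies between them). The values closest to the printed H0 crossing probabilities were kept.

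| Statistic | Type I error | Power at 0.51 |
|---|---|---|
| Unpooled Z | 0.0481 | 0.823 |
| Pooled Z | 0.0462 | 0.810 |
| Simple difference | 0.0489 | 0.840 |
| Plan | 0.048 | 0.813 |

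The unpooled Z also returns the plan's H0 increments (0.0150, 0.508, 0.033, 0.444). If 0.71 is instead treated as a known constant and the printed counts are applied directly, type I error is 0.0154 and power 0.8865, which does not match. The plan's figures are therefore those of a design with a random control sample of 93.

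**Step 2: no PBM effect, shifted case mix.** Keep the controls at 0.71, set p = 0.71 − d, and leave everything else unchanged. The values of d are assumptions.

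| Shift d | Rate without PBM | P(efficacy), controls random (range over three statistics) | P(efficacy), printed counts, control rate fixed at 0.71 |
|---|---|---|---|
| 0 | 0.71 | 0.046–0.049 | 0.015 |
| 3 points | 0.68 | 0.10–0.11 | 0.052 |
| 5 points | 0.66 | 0.15–0.17 | 0.10 |
| 10 points | 0.61 | 0.35–0.39 | 0.33 |
| 13 points | 0.58 | 0.50–0.54 | 0.53 |

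The random-control column is the one to read, because it starts from the plan's own 0.048. A 5-point shift multiplies the error by about 3 (0.162/0.048 = 3.4, unpooled Z) and a 10-point shift by about 8 (0.369/0.048 = 7.7). Relative to the 20-point target effect these shifts are 5/20 = one quarter and 10/20 = one half.

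**Step 3: a shift the other way.** Suppose case mix raised the expected rate by 5 points and PBM still lowered it by 20. The observed gap would be 20 − 5 = 15 points. The same calculation at a 15-point gap gives 0.60–0.64, against a planned power of 0.813.

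**Step 4: does Section 10.2.2 fill the gap?** It compares grade, duration and engraftment in one-to-one matched patients. It does not name grade 3 or above (yes/no) as an outcome, does not use all 93 controls, and is not referred to in 10.2.1.

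**The case against.** - **Control uncertainty is already counted.** This is correct. Section 10.1 treats the 93 as an arm, so their sampling error is within the 0.048. A reader might infer that the plan tests against a historical rate assumed known; it does not. What remains uncounted is systematic difference between the groups.
- **A case-mix-controlled check is already planned.** Largely fair. Mucositis grade contains the grade 3 threshold, counts by grade will be reported, and controls are to be selected before the biostatisticians receive the grade 3 outcome. The remaining gap is narrow: the binary endpoint is not named there, and the result has no stated bearing on the primary conclusion.
- **The shift is hypothetical.** Also fair. The controls are described as having similar conditions, and no rates by stratum are given. The documents do not say whether repeat transplants carry a higher or lower rate; a higher rate would cost power rather than create false efficacy.
- **A reader might infer that a small shift makes a false positive likely.** The figures do not support that. A 3-point shift gives 10–11%, and passing 50% takes about 13 points, roughly two thirds of the target effect (13/20 = 0.65).
- **Requiring the adjusted estimate to agree before efficacy is declared** would create a second criterion, which can only lower the planned power of 0.813. An adjusted test cannot be sized from these documents. That argues for a supportive analysis, not a gate.

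**Conclusion.** The concern holds in a limited form. The primary efficacy conclusion is unadjusted, the control and trial populations are defined differently, and the adjusted analysis that the plan does contain is not tied to the primary endpoint. On the plan's own design, an assumed favourable shift of 5 to 10 points raises the chance of a false efficacy claim from about 5% to about 15–39%; an unfavourable shift reduces power.

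These figures rest on three assumptions: the size and direction of the shift, which the documents do not give; critical values inferred from the printed boundaries; and independent binomial outcomes. The documents do not show that a shift exists, and they do not show that the stated type I error and power are wrong. Those reproduce closely when the two populations are exchangeable. The point is a gap in the supporting analysis, worth closing because the data are already to be collected.

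**What to change.** Keep the boundary rule in Section 10.1 as the formal decision, with its sample size and looks unchanged. Add to Section 10.2.1:

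- a pre-specified supportive logistic regression of grade 3 or above (yes/no) on group, PBM versus all 93 controls, adjusted for age, sex, primary disease and conditioning regimen;
- disease and regimen grouped into a few categories fixed before outcomes are seen, or a penalised (Firth) fit, because the controls supply only 93 − 66 = 27 non-events and the trial may stop at 40 patients;
- the standardised risk difference with its confidence interval, reported beside the boundary result;
- a statement that a boundary success whose adjusted estimate is null or materially smaller will be reported as possibly explained by case mix, with the meaning of materially smaller written down in advance.

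The cost is a little more analysis. No new data are needed, provided the four variables that Section 10.2.2 uses for matching are held for all 93 controls. The downside is that a positive boundary result may need a more cautious conclusion.

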#### 10.2.2 Statistical analysis for the secondary objective

*To compare clinical manifestations associated with the development of oral mucositis between those treated with daily PBM and a matched control. Clinical factors to include: mucositis grade, duration, and days to engraftment.*

*Hypothesis 2: Children and adolescents treated with extra-oral PBM will develop lower grade mucositis, with shorter mucositis duration (days) than the comparison matched control.*

Patients enrolled in the PBM study will be matched to a transplant control that did not receive PBM by age, sex, primary disease and transplant regimen. For a patient receiving PBM, the patients with the same sex, primary disease and transplant regime will be used as the candidate pool. The patient in the pool with the smallest difference of age is selected as matching. If there is more than one patient in the pool that satisfies the smallest difference of age, a reproducible random number generator will be used to randomly select one patient out of the multiple candidates.

The patient identifier, age, sex, primary disease and transplant regime for the patients without PBM in the historical data will be sent to the Biostatisticians without the outcome of development of grade 3 mucositis. The patient identifier for the selected patients in the historical data will be determined. Then other information for these patients will be obtained for analysis.

The two groups will be compared from day 1 of conditioning regimen until engraftment (2 consecutive days of an ANC>500) or Day+20.

The PBM group and the historical group without PBM will be compared on mucositis grade, duration of mucositis (number of days) and days from cell infusion to engraftment. We will compute the descriptive statistics (mean, standard deviation, median, and range) of the duration of mucositis and days to engraftment. We will also compute the descriptive statistics (count and percentage) of mucositis grade. To compare the clinical variables between the PBB and matched control groups, we will use generalized linear model with the variables for matching as covariates. The difference will be assessed by two-sided Wald tests with type I error rate  $< 0.05$ . For the duration of mucositis, the subset of patients who developed Grade 3 mucositis will be compared with their match control patients with similar methods described above.

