**Table Summary of Photobiomodulation Therapy Delivered**

Case number	Days on protocol a	Days received treatment b	Total cumulative dose c (J/cm  )	Treatment site = right face	Treatment site = midline face	Treatment site = left face	Treatment site = left neck	Treatment site = midline neck	Treatment site = right neck

aDays on protocol defined as from the first day of hematopoietic cell transplantation conditioning through engraftment

bDays received treatment defined as days with treatment during any of the on-protocol days

cCummulative dose define as single treatment dose multiplied by the number of treatment sites (up to 6 in total) for each treatment session

Efficacy will be assessed with assessment of grade 3 mucositis development from day 1 of conditioning to Day +20 of transplant or engraftment as a binary outcome (yes/no)

[figure not shown]
Daily observation: The observation of oral mucositis will be conducted by non-study staff and conducted as clinical care by the nurse, advanced practice provider and/or physician.

Assessment: Each patient or parent proxy will complete the Children's Mucositis Assessment via ipad along with documentation of mucositis grade, duration, days of nutrition support, use of narcotics, positive oral and blood cultures.

Each patient will be matched and compared to a previously treated patient. The comparison will be matched on primary disease, conditioning regimen, age and sex, with comparison of treatment variables of mucositis grade, duration, pain medications, days of nutritional support, blood and oral cultures, to day +20 or engraftment (depending upon which occurs first).

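### Does the silence of Section 10.2.2 on re-used and missing matched controls undermine the secondary Wald tests?

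*Combined protocol and SAP*

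**What the plan says.** Section 10.2.2 defines a candidate set separately for each treated patient: "For a patient receiving PBM, the patients with the same sex, primary disease and transplant regime will be used as the candidate pool". Within that set, "The patient in the pool with the smallest difference of age is selected as matching", and ties on age are broken at random with a reproducible generator. Selection comes before outcome data: the matching variables "will be sent to the Biostatisticians without the outcome of development of grade 3 mucositis", then "The patient identifier for the selected patients in the historical data will be determined", and only afterwards is the remaining information on those patients collected. For the comparison of grade, duration and days to engraftment, "we will use generalized linear model with the variables for matching as covariates", with two-sided Wald tests at 0.05. No pair term, cluster term, weight or robust variance is named.

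Section 4.1 adds, after the treatment summary table, "Each patient will be matched and compared to a previously treated patient", which presumes that a match can be found. Section 10.1 "identified 93 first allogeneic transplant patients with similar conditions" for the primary design and states that "The complete historical control sample will be used in both the interim analysis and final analysis". Section 10.2.2 speaks only of the historical data and does not declare those 93 patients to be the matching pool.

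**The concern.** The matching procedure is otherwise specific enough to program, so the three omissions stand out: no step removing a chosen control, no rule for an empty candidate set, and no rule for a control shared by several PBM patients. Followed patient by patient, the text lets one control be chosen repeatedly. If each pair then contributed a row, one historical patient would count as several independent observations, the standard error would be too small, and the nominal 5% test would reject too often.

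The tests at stake carry Hypothesis 2 (lower grade, shorter duration). The same silence extends to the grade 3 duration subset in 10.2.2 and the autologous matching in 10.2.3. Controls are fixed without the grade 3 outcome, but the row rule could in principle be settled after outcomes are seen.

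**Working it through.** **Inputs from the documents.** 66 evaluable PBM patients (Section 4.1); two-sided Wald test at 0.05, so critical value 1.96 (Section 10.2.2). The only stated figure for this analysis is that 0.05. No power, effect or sample size is given for it.

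**Assumptions.** Pool size (93 from Section 10.1 as one case, larger pools as others), number of disease and regimen categories, age roughly uniform up to 21 years, no treatment effect.

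**Step 1: how often controls are re-used.** In simulated nearest-age matching with 10 exact-match strata, a pool of 93 gives 65.4 pairs but only 42.0 distinct controls. The variance of the control mean is 2.07 times what independent rows would imply.

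**Step 2: effect on the test if rows are repeated.** Ignoring covariates, with *m* control rows and inflation factor *v*:

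ratio of true to assumed variance = (1/66 + *v*/*m*) / (1/66 + 1/*m*)

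- Pool 93: (0.01515 + 2.07/65.4) / (0.01515 + 0.01529) = 0.04680/0.03044 = 1.537. The true SD is √1.537 = 1.240 times the assumed one, so the effective cut-off is 1.96/1.240 = 1.581 and the rejection rate is 2Φ(−1.581) = 11.4%.
- Pool 186 (*m* = 65.8, *v* = 1.53): ratio 1.265, cut-off 1.742, rejection 8.1%.
- Pool 372 (*m* = 66.0, *v* = 1.27): ratio 1.135, cut-off 1.840, rejection 6.6%.

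Full simulation of the covariate-adjusted model in the same settings (3,000 null trials each) gives 12.1%, 8.9% and 7.0%, slightly above the hand figures. The mechanism is therefore confirmed.

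**Step 3: the three readings compared.** Null simulation, 4,000 trials per setting, 66 PBM patients, pool 93, residual SD 5 days. The range covers six category settings; the sparsest (8 diseases by 6 regimens, equal frequencies) is in brackets.

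| Reading | Rejection, continuous outcome | SD of estimate (days) | PBM patients unmatched |
|---|---|---|---|
| Re-use, a row per pair | 12.2–13.1% (9.7%) | not compared | 0–13 (25) |
| Re-use, each control once | 5.1–5.8% (5.8%) | 0.98–1.11 (1.21) | 0–13 (25) |
| Without replacement | 4.9–6.2% (5.8%) | 0.87–1.07 (1.23) | 0–22 (32) |

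For reference, 66 against 66 independent patients gives an SD of 5·√(2/66) = 0.870 days. Other simulated settings with repeated rows and a pool of 93 ranged from 10.0% to 13.5%. With a pool of 300 the rate was 6.7–7.8%. If the trial stopped at 40 patients (pool 93), repeated rows gave 9.1–9.9% (8.0%).

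**Step 4: which reading the text supports.** Section 10.2.2 collects data for the selected patients, then compares a PBM group with a historical group in a model that adjusts for the matching variables and carries no pair term. The ordinary data set for such a model has one record per person. Nothing tells the analyst to duplicate a record. Only the first row of the table fails to hold the level.

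**The case for a change.** The best case for amending is that the options differ in error rate, in precision and in who is analysed; that outcomes are released once the control list is fixed; and that a few sentences would close the gap. A reference to the matched controls of the patients with grade 3 mucositis also implies that pair links are kept, so repeated rows are not excluded.

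Much of this stands. The omissions are real, no other section supplies the rules, and the direction of the error under repeated rows was the same in every setting tried. It does not carry the conclusion, for three reasons.

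- The harm depends on an analyst treating one patient as several independent ones, which the plan does not instruct. It would also be visible, because about 42 historical patients would be presented as about 65.
- Choosing between the two sound readings is a trade-off. Matching without replacement tends to be more precise, but it leaves more patients unmatched and gives poorer age matches (mean gap 2.7 against 1.5 years with three diseases by two regimens, equal frequencies). A covariate model on the complete historical sample had the smallest SD (0.81–0.85 days), but that is an additional analysis needing further chart abstraction.
- Some patients may have no exact match under either sound reading. Reporting them as unmatched is routine.

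One residual weakness is not about the missing rules. For a grade 3 yes/no outcome in the sparsest setting, the Wald test rejects about 8% even with each control used once. Section 10.2.2 lists mucositis grade rather than that binary outcome, and ordinal grade was not simulated.

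**Conclusion.** The concern does not call for a change. Section 10.2.2 omits a replacement rule, an empty-pool rule and a row rule, but this is missing detail that a trial statistician would ordinarily fill soundly: each historical control enters once, and PBM patients without a candidate are reported as unmatched. The same practice covers the grade 3 duration subset and the autologous matching in 10.2.3.

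On either sound reading the continuous-outcome tests reject about 5% to 6% under the null. The inflation to roughly 10% to 13.5% arises only with re-use and repeated rows and a pool of 93, and shrinks to about 7% to 8% with 300. Those sizes rest on an assumed pool and assumed categories, so they are not properties of this plan. The precision cost of sharing controls has no stated target to miss, since no power is claimed for this comparison. Selection is made without the grade 3 outcome, and the primary analysis uses the whole historical sample and is untouched.
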